**Table 2: Time Point Based Expected Adverse Reactions During Niacin Administration**

	Time (hours after Niacin administration)
--	---

Expected adverse reactions (%)	1	2	3	4	5	6
Headache	20	0	0	0	0	0
Flushing	100	100	100	50	50	0
Feeling warm	100	100	100	60	20	0
Nausea	20	20	0	0	0	0
Vomiting	20	20	0	0	0	0
Stomach Ache	20	20	0	0	0	0
Diarrhea	20	0	0	0	0	0
Tingling	20	20	0	0	0	0
Light-headedness	20	0	0	0	0	0
Itchiness	100	100	60	40	0	0
Rashes	20	20	20	20	0	0

If the rate or severity of these events exceeds the rate or severity anticipated in the protocol or FDA-approved package insert, the events will be classified and reported as though they are Unanticipated Problems.

Because we anticipate that other mild symptoms may occur in the course of participation in the protocol that are unrelated to study drug or participation, we will not submit Unanticipated Problems for mild signs/symptoms (CTCAE Grade  $\leq 2$ ), such as rhinorrhea, nasal congestion, watery eyes, cough, lightheadedness, fever blister, etc., that occur infrequently ( $\leq 10\%$ ). Such events will be reported at the time of the IRB Annual Review.

**Data safety monitoring board (DSMB):** A DSMB will be assembled for oversight of this protocol by the Clinical Director, NICHD, with membership and scope determined by applicable institutional guidelines. The DSMB will meet to evaluate all serious adverse events and will at a minimum convene yearly. The DSMB will examine whether there is evidence of safety for niacin administration. The DSMB will review adverse event questionnaire data, and reports of side effects from all visits. These reports will also be supplemented by a manual review by the investigators, who will add any other events not captured by these systems. Results will be presented as an A vs. B analysis prepared by the data manager. The DSMB will be asked to prepare a detailed report to

supply to the IRB that describes any adverse events discussed, and that explains the DSMB's vote to allow the study to continue or recommendation to end the study.

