**Table 2: Suppression of FFA <2 mEq/L by Niacin**

Group	Number of Subjects	Percentage of measurements post niacin with FFA <0.2 mEq/L
250 mg q 2H	2	11.5%
500 mg q 2H	5	43.1%
500 mg q 1H	5	67.5%

Adverse events during Dose Establishing Study 2 were largely as expected. All participants reported flushing or warmth, 60% tingling or rash, and 20-40% abdominal discomfort, nausea, or emesis.

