**Data Table 3: Reported Adverse Events During Niacin Dose-Finding Study 2**

Expected adverse reactions (%)	500 mg Niacin every hour (n=5)				
	Time (hours)				
	0	1	2	3	4
Headache	0	20	0	0	0
Flushing	0	100	40	40	0
Feeling warm	40	100	40	20	20
Nausea	20	20	40	0	20
Vomiting	0	20	0	0	20
Stomach Ache	20	40	20	20	20
Diarrhea	0	0	0	0	0
Tingling	0	60	20	0	0
Light-headedness	0	0	0	0	0
Itchiness	0	60	40	20	0
Rashes	0	0	0	0	0

Note: niacin doses administered at time 0, 1, 2, and 3. Time 0 data reflect reactions before the first dose was administered. The symptoms at hour 4 were of short duration with only moderate severity. The symptoms reported at earlier hours were also of mild or moderate intensity and, with the exception of feeling warm or flushing, of short duration. All symptoms had resolved completely by the end of the 4th hour.

We therefore will initiate the main study protocol.

During the main study, two sets of GH stimulation tests will be performed on two consecutive days. On one day, the testing will be performed in conjunction with four hourly doses of niacin 500 mg, and on the other day with four doses of a placebo, with the order (niacin first day or second) randomly determined. Subjects will not receive sex hormone “priming” pretreatment (which is used by some clinicians to overcome the naturally lower occurring GH concentrations found in prepubertal children) due to the design of the study; no protocols have established methodology for priming when performing GH stimulation testing on sequential days. We were concerned that administration of sex-steroids could differentially affect the first stimulation test compared to the second. Additionally it might be difficult to assure compliance with the medication as it would be taken at home prior to the admission. Furthermore this protocol will be restricted to

prepubertal and early pubertal subjects to limit the degree of sex hormone influence. It should also be noted that the vast majority of pediatric growth hormone testing performed in the US is done in the absence of such sex steroid priming.

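### For four of eleven niacin reactions, the expected rates that trigger Unanticipated Problem reporting are below rates the protocol already reports for the hourly regimen; the phlebitis entry and the symptom collection schedule also do not fit the main study

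*Combined protocol and SAP*

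**What the plan says.** The section on waiver of reporting to the IRB has two lists of anticipated adverse events. The first, for events above the rate known in this population, gives an expected frequency for phlebitis after an intravenous catheter as 20% with one subject in brackets, and refers reactions to niacin to the time-point table. That table (Table 2: Time Point Based Expected Adverse Reactions; an earlier table on FFA suppression has the same number) covers 11 reactions at hours 1 to 6. Four of its rows are "Nausea 20 20 0 0 0 0", "Vomiting 20 20 0 0 0 0", "Stomach Ache 20 20 0 0 0 0" and "Tingling 20 20 0 0 0 0".

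The rule beneath it reads "If the rate or severity of these events exceeds the rate or severity anticipated in the protocol or FDA-approved package insert", in which case "the events will be classified and reported as though they are Unanticipated Problems". Under Adverse event reporting, non-serious unanticipated problems go to the IRB within 14 days.

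Data Table 3 gives hourly reaction rates for the five children of Dose-Establishing Study 2, dosed at hours 0, 1, 2 and 3. The text before it states that all had flushing or warmth, "60% tingling or rash, and 20-40% abdominal discomfort, nausea, or emesis". The main study uses the same four hourly doses.

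Adverse event reporting and Appendix D schedule the symptom questionnaire hourly in the dose-establishing study, but only once, at the end of the stay, in the main study.

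**The concern.** A reporting threshold should separate what is already known from what is new. Here, some thresholds are below what the protocol has already recorded for the regimen it goes on to use. If the main study reproduced those rates, familiar and mostly short-lived symptoms would be filed as Unanticipated Problems, and a real signal would be harder to see among them. The phlebitis entry leaves open whether the second case or the eleventh in 50 children is the excess. Limits set by the hour cannot be applied if symptoms are not scheduled for recording by the hour.

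**Working it through.** **Inputs.** Limits: the time-point table in the waiver section, hours 1 to 6. Hourly-regimen rates: Data Table 3, hours 0 to 4, n = 5, with hour 0 before any dose. Two-hourly rates: Table 1 (Study 1), 250 mg (n = 2) and 500 mg (n = 5). Main-study size: 50 studied, 40 completers (Determination of Sample Size).

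**Step 1: where the limits come from.** The protocol states no derivation. For each of the 11 × 6 = 66 cells I compared the limit with the larger of the two Study 1 rates. In 57 cells they are equal, in 9 the limit is higher, and in none is it lower. The six-hour grid is also Study 1's; main-study sampling ends at hour 4. That the table was built from Study 1 and not updated is an inference from this pattern.

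**Step 2: limits against the hourly regimen.** There are 11 × 4 = 44 cells. The observed rate is above the limit in 7, equal in 20 and below in 17. The seven are:

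| Reaction | Hour | Limit % | Study 2 % | Excess, children of 5 | Rate at hour 0 % |
|---|---|---|---|---|---|
| Tingling | 1 | 20 | 60 | 2 | 0 |
| Stomach ache | 1 | 20 | 40 | 1 | 20 |
| Stomach ache | 3 | 0 | 20 | 1 | 20 |
| Stomach ache | 4 | 0 | 20 | 1 | 20 |
| Nausea | 2 | 20 | 40 | 1 | 20 |
| Nausea | 4 | 0 | 20 | 1 | 20 |
| Vomiting | 4 | 0 | 20 | 1 | 0 |

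**Step 3: other readings.**
- Hours counted from the latest dose, so that every Study 2 hour is set against the hour-1 limit: three cells exceed (nausea 40 v 20, stomach ache 40 v 20, tingling 60 v 20).
- Hour-0 rates subtracted: two cells exceed (tingling hour 1, vomiting hour 4).
- Tingling at hour 1 exceeds on both, and in Step 2.

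**Step 4: precision.** With n = 5, exact 95% intervals are 0.5% to 72% for 20%, 5% to 85% for 40%, and 15% to 95% for 60%.

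**Step 5: how the limits would behave if hourly counts existed.** With 50 children, a 20% limit is crossed at 11 or more events. The binomial probability is 0.42 at a true rate of 20% and 0.998 at 40%; with 40 children (9 or more) it is 0.41 and 0.994. A 0% limit is crossed by one event: at a true rate of 2%, 1 − 0.98^50 = 0.64, or 1 − 0.98^40 = 0.55. The true rates are assumptions.

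**Step 6: phlebitis.** 1 / 0.20 = 5, so rate and count agree for five children. In 50 children, 0.20 × 50 = 10, while 1 / 50 = 2%; in 40, the figures are 8 and 2.5%.

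**The case against.** Most of the table is not in conflict: 37 of 44 cells are met or not reached, and 7 of 11 reactions show no excess. Six of the seven excesses are a single child, and nausea and stomach ache were each at 20% before any drug. This stands and limits the size of the point. It does not remove tingling.

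The trigger is also wider than the table. It cites the package insert, which is not in the documents, and the Study 2 results are themselves in the protocol, which calls them largely as expected. Under a generous reading those rates are already anticipated. But the first waiver list sends niacin reactions to the time-point table alone, so the text still needs reconciling.

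Limits that are too low produce extra reports; they are not stopping rules. All adverse events are recorded, serious events have their own timelines, and the DSMB reviews questionnaire data. This also stands.

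For phlebitis, the operative wording concerns a rate, neighbouring entries are percentages, and 20% can be applied at any size. The bracketed count is probably a leftover, but it contradicts the rate in the main study.

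A reader might infer that flushing, warmth and itching can never trip the rule because eight cells are 100%. The documents do not support this: limits fall at later hours (flushing to 50% at hour 4, itchiness to 60% at hour 3), and severity is a separate criterion, graded mild to severe in Appendix D. What is missing is a stated reference level for severity.

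**Conclusion.** The point holds as an internal contradiction of limited size: 7 of 44 cells, 4 of 11 reactions, with tingling at hour 1 the only cell that exceeds by more than one child. The consequence is over-reporting of expected symptoms. The phlebitis rate and count agree only for n = 5. That the five are a dose-finding group is an inference from the cap of five per group. Separately, the hourly limits have no scheduled hourly data in the main study.

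Two stronger readings are tempting. One is that the triggers as a whole cannot distinguish expected from unexpected harm; the 37 unaffected cells, the severity criterion and the separate safety review argue against that. The other is that crossing is almost certain in 40 or 50 children. That treats rates from five children as true and assumes hourly counts that the main study does not schedule. The interval for tingling starts at 15%, below its own 20% limit, so the near-certain figures in Step 5 are conditional illustrations and not predictions.

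**What to change.** With the IRB, reconcile the time-point table, the phlebitis entry and Data Table 3:

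- Set expected rates no lower than those already reported for the hourly regimen. On the present grid this changes seven cells: nausea hour 2 to 40% and hour 4 to 20%; vomiting hour 4 to 20%; stomach ache hour 1 to 40% and hours 3 and 4 to 20%; tingling hour 1 to 60%.
- State the limits on the time scale on which main-study symptoms are collected, or align the collection with the limits. Hourly percentages do not give the share of children affected over a day or a stay, so the first option needs the child-level Study 2 records. The second needs the questionnaire given more often.
- Where the rate limit is 100%, state what observed severity is compared against.
- Give phlebitis as a single rate.

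The cost is a protocol text change plus a look back at existing Study 2 records, or extra questionnaires. The downside is that some limits rise, and they would rest on five obese children given niacin without arginine or L-dopa. The protocol lists nausea and vomiting among the effects of both added drugs, so the revised limits should be described as provisional.

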### **Data Analysis**

Primary research outcome will be niacin-induced changes in arginine and L-dopa stimulated GH concentrations, measured as both area under the curve and peak values, in the overweight group compared with the control group. Secondary research outcomes will include changes in free fatty acid, glucose, and insulin concentrations during the GH stimulation tests. Since non-completion of the study is expected to be due to technical failures (e.g., nonfunctioning IVs) rather than subject factors, all analyses will be limited to subjects who complete both placebo and niacin studies. We do expect that some members of the control group will not reach a peak GH concentration of 7 ng/mL during the stimulation testing. We will report all control subjects in the final analyses. Analyses will be performed with age, Tanner stage, and initial BMI-SDS as covariates. Furthermore, tertiary analyses will also be performed to compare subjects in the Tanner I, Tanner II, and Tanner III groups to determine if any differences exist among these pubertal development stages. This analysis will be for exploratory purposes only; the study is not powered for this subgroup analysis. Additionally if any members of the control group have abnormally elevated lipid levels, we will specifically examine these subjects and their growth hormone concentrations. The primary outcome analysis will therefore be a repeated measures ANCOVA with subject group (obese and control) as the between factor, treatment (niacin or placebo) as the repeated measure, GH concentration (peak and AUC) as the outcome variables, and age, sex, and Tanner pubertal stage as covariates. We will also model the subject group by treatment interaction but no other interaction terms will be entered into the primary analysis.

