### **Determination of Sample Size**

Using data from the available studies that used acipimox, we performed power calculations based on the difference in effect on peak GH secretion found with and without use of acipimox in

obese adults. Following acipimox, this cohort showed an increase of 10.3 micrograms per liter in peak GH concentrations with a standard deviation of 6.1. Thus, at a power of .80 and an alpha of .05, the sample size necessary to detect a 10 microgram per liter difference in GH secretion is 14 in each group (e.g. obese versus control), and at a power of .95 and an alpha of .05, the sample size necessary to detect a 10 microgram per liter difference in GH secretion is 22 in each group. Given these calculations, we will aim for 20 subjects per group who complete all aspects of the study.

Allowing for 20% of subjects to fail to complete the main study for various reasons, the total number of subjects needed to be studied is 50 (25 in each group). We expect that we will need to screen no more than 66 children to find the 50 who meet the inclusion and exclusion criteria. Subjects will be randomized with the assistance of the NIH Investigational Drug Management and Research Section (IDMS); we anticipate sex and race/ethnicity to be similar in each study arm. For the pilot dose-finding studies, we will study no more than 5 per group (15 total) and screen at most an additional 10 subjects who do not qualify for these studies.

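### Peak GH and AUC are both primary with no rule for combining them, so type I error is not held at 5% if significance on either measure counts

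*Combined protocol and SAP*

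**What the plan says.** The Data Analysis section gives the primary outcome as "niacin-induced changes in arginine and L-dopa stimulated GH concentrations, measured as both area under the curve and peak values", compared between the overweight and control groups. The primary model, a repeated measures ANCOVA, then takes "GH concentration (peak and AUC) as the outcome variables". On model terms it adds: "We will also model the subject group by treatment interaction but no other interaction terms will be entered into the primary analysis". The section states no significance level, no order between peak and AUC, and no rule on whether one or both must be significant.

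Alpha appears only under Determination of Sample Size, where "we performed power calculations based on the difference in effect on peak GH secretion". The source cohort "showed an increase of 10.3 micrograms per liter in peak GH concentrations with a standard deviation of 6.1", and sample sizes are quoted "at a power of .80 and an alpha of .05" and "at a power of .95 and an alpha of .05". No effect size or standard deviation for AUC is given anywhere.

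In the Specific Hypotheses, the comparison of obese with control children and the expected restoration by niacin are both framed on peak stimulated GH. One sentence, on augmentation in the short controls, speaks of GH secretion without naming a measure. AUC is not mentioned there.

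**The concern.** Two measures have equal primary standing and nothing says how their results combine. The trial could show a significant interaction on one and not the other, and the plan does not say whether that is a positive primary result. The reading could then be chosen after the data are seen. If either measure is enough, there are two chances of a false-positive primary claim, and the .05 used for planning does not describe that claim.

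A separate consequence is that AUC has primary status with no stated power, so a non-significant AUC result would be hard to interpret.

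**Working it through.** **Inputs.** From the documents: two primary measures (Data Analysis); alpha .05, target difference 10 µg/L, SD 6.1 and 20 completers per group (Determination of Sample Size). Assumed: two-sided tests, because sidedness is not stated; .05 applied to each measure, because the Data Analysis section gives no alpha; and a range of peak-AUC correlations, because none is given.

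**1. The plan's own figures.** The sample size section gives 14 per group for 80% power and 22 per group for 95%. With n = 2 × SD² × (z for alpha + z for power)² / difference²:
- 80%: 2 × 37.21 × (1.960 + 0.842)² / 100 = 5.8, so 6 per group (7 by t-test).
- 95%: 2 × 37.21 × (1.960 + 1.645)² / 100 = 9.7, so 10 per group (11 by t-test).

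The stated figures are therefore not reproduced as per-group numbers with SD 6.1. The t-test totals over both groups are 14 and 22. With SD 6.1 × √2 = 8.63, which the documents do not state, the t-test gives 13 and 21 per group. That discrepancy is a separate matter. It is noted here because power is shown below under both SDs.

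**2. Error if either measure counts.** Under no effect on either measure, P(either) = 1 − P(|Z1| ≤ 1.96 and |Z2| ≤ 1.96). For independent tests this is 1 − 0.95² = 9.75%. The upper bound under any dependence is 0.05 + 0.05 = 10%.

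**3. Error if both are required.** P(both) = 0.05 + 0.05 − P(either). It can never exceed 5%.

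| Assumed correlation | Either counts | Both required |
|---|---|---|
| 0 | 9.75% | 0.25% |
| 0.5 | 9.1% | 0.9% |
| 0.7 | 8.3% | 1.7% |
| 0.8 | 7.8% | 2.2% |
| 0.9 | 7.0% | 3.0% |
| 0.95 | 6.5% | 3.5% |

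Simulated t-tests with 20 per group (200,000 replicates) gave 9.8%, 9.1%, 8.3%, 7.8%, 7.1% and 6.5% in the same order for the either-counts column. Small-sample behaviour therefore does not change the picture.

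**4. Splitting alpha.** At .025 each, independent tests give 1 − 0.975² = 4.94%, and the total cannot exceed 5%. With 20 per group and a difference of 10 µg/L, t-test power for peak is:

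| SD | Alpha .05 | Alpha .025 |
|---|---|---|
| 6.1 | 99.9% | 99.7% |
| 8.63 | 94.6% | 90.3% |

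Power for AUC cannot be computed at either level.

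**The case against.** The strongest reply is that the plan never says one significant measure is enough. Its wording, "measured as both area under the curve and peak values", can be read as requiring both. If so, or if peak were tested first, there is no inflation. This stands, and it is why the conclusion is conditional. A reader might infer that the false-positive rate of this trial exceeds 5% outright; the documents do not support that. They leave the rule open.

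Three other inferences should be resisted:
- **That powering peak alone raises the false-positive rate.** It does not. It leaves power for AUC unknown and indicates which measure should lead.
- **That the plan commits to testing each measure at .05.** That level is stated only for the peak power calculation. Applying it to AUC is an assumption, though a natural one.
- **That there are four primary tests, peak and AUC for each of arginine and L-dopa.** The Introduction gives a physiological reason for using two stimuli, but the primary model lists two outcome variables and no stimulus factor. No primary test per stimulus is described.

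It can also be said that peak and AUC come from the same GH curve, so their correlation is probably high. That is plausible. It would put the error near the lower end of the range (7.0% at 0.9, 6.5% at 0.95), but still above 5% for any correlation below 1.

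Finally, the trial is called a pilot. This lowers the consequence but does not supply a decision rule. The Introduction also says the investigators wanted the study powered so that significant results were possible, and the Data Analysis section labels only the Tanner-stage comparison exploratory.

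**Conclusion.** The point holds in conditional form. Peak and AUC are both primary, no decision rule connects them, and the only alpha, the only power calculation and the hypotheses that name a GH measure all concern peak. If either measure counts, type I error is about 6.5% to 9.1% for correlations of 0.95 to 0.5, and 9.75% if the tests are independent. These figures assume two-sided tests at .05 on each measure and correlations that are not in the documents. If both were required, the error would not exceed 5%. Power for AUC is unknown on any reading. The gap does not invalidate the trial, but it should be closed before the data are analysed.

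**What to change.** In Data Analysis, name peak GH over the whole test as the single primary outcome, tested by the group-by-treatment interaction at two-sided .05. Make AUC the first secondary outcome, tested at the same level only if peak is significant. Peak is the choice because it is the measure in the power calculation and the hypotheses. The interaction is the choice because the section already defines the primary comparison as the niacin-related change in one group against the other. Saying that peak is taken over the whole test also settles whether it is per stimulus.

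The change takes a sentence or two and no more participants. The downside is that a significant AUC with a non-significant peak can no longer be called a primary success. Requiring both measures, or testing each at .025, would also control the error. But either would keep AUC as a primary measure with no stated effect size or power.
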